5.2.4 Early Discontinuation or End of Study Visit

Subjects will be discharged from the study after completion of an EoS visit for follow-up assessments which will happen 16 weeks after the IMP dosing +/- three days or earlier in case of early discontinuation (ED). The principal investigator will inform the family doctor and pain clinic (if applicable) with details of participation in the clinical study and any relevant information which may help the treating physician in the management of their patient.

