5.1 General Considerations

All statistical analyses will be performed using the SAS® software version 9.4 or higher.

For Part A, only listings will be provided. For Part B, tables, figures and listings will be provided.

5.1.1 *Outputs Presentation*

5.1.1.1 *Tables Header*

Depending on the type of data, the summary tables will be presented as follows:

- For disposition, demographic data and baseline data description: by treatment group and overall,
- For efficacy and safety data: by treatment group and all Dysport.

5.1.1.2 *Presentation of Treatment Group*

For Part A, listings will be displayed using the following treatment group labels, in the order presented:

Long label	Short label
Lidocaine 2.5mg/injection site	Lidocaine
Placebo	Pbo

For Part B, Tables, Figures and Listings (TFLs) will be displayed using the following treatment group labels, in the order presented:

Long label	Short label
Placebo	Pbo
Dysport 2.5U/Injection site	Dysport 2.5U*
Dysport 10U/Injection site	Dysport 10U*
Dysport 20U/Injection site	Dysport 20U*

* Per injection site

When specified, tables will also be described by total dose received in the painful injection area and the total dose received in the painful area divided by the painful area.

5.1.1.3 *Presentation of Visits / Timepoints*

Summaries by visit will be presented using visit number as collected in the electronic Case Report Form (eCRF).

Visits in the TFLs will be presented as follows and in that order:

Part	Long Visit Name	Short Name
	Screening	Scr
Part A	Injection test 1 (Day -21 max)	Inj1
	Injection test 2 (Day -14 max)	Inj2
Part B	Baseline (Day -7 Day -1)	Bsl
	Day 1 Pre-dose	D1 Pre-dose
	Day 1 Post-dose	D1 Post-dose
	Day 2 Day 7	D2 D7
	Week 2	W2
	Week 4	W4
	Week 6	W6
	Week 8	W8
	Week 10	W10
	Week 12	W12
	Week 14	W14
	End of Study	EOS

5.1.2 *Descriptive Statistics*

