5.8.7 *Physical Examination*

Physical examinations include a general inspection, assessed at screening, baseline, day 1 pre-dose, week 6 and end of study and a scar physical examination, assessed at week 6.

Scar physical examination will be coded using the latest version of MedDRA in effect within IPSEN at the time of database lock

The following listings will be provided on Part B:

- A listing of physical examination data,
- A listing of scar physical examination data,
- A listing presenting subjects with at least one physical examination abnormality.

5.8.8 *Pregnancy tests*

Urine pregnancy tests will be performed at screening, at day 1 pre-dose and at end-of-study visit.

A listing with the date of examination, the status of the examination (performed/not performed) and the result (positive/negative) will be provided by treatment group, subject and examination date.

5.9 *Pharmacokinetics (if applicable)*

Not applicable.

5.10 *Anti-drug Antibodies (if applicable)*

Not applicable.

6 *DATA HANDLING*

6.1 *Visit window*

Visits can occur +/- three days around the scheduled date.

6.2 *Unscheduled Visits, Retest, Withdrawal Visit,*

All listings will include retests and unscheduled visits, while for the description by visit in the tables, only the scheduled visits according to the protocol will be described.

Unscheduled visit and retest measurements will be used to provide a measurement for a baseline data or endpoint value (e.g. worst value), if appropriate according to their definition. These measurements will also be used to determine abnormal laboratory, vital signs values or ECG.

If a value requires a retest (for laboratory values, vital signs and ECG) the closest non-missing reliable value to the scheduled visit will be used in the summary tables. An assessment will be considered reliable if it is performed without any technical problem and if the result is within the range of likely values.

Subjects who have withdrawn early from the study have their last assessment entered as visit 90 in the eCRF. By convention, for these subjects, the visit number will be reassigned to the next empty visit number (i.e. if a subject has Visit 1, 2, 3 and 90 entered in the database, the visit number 90 will be reassigned to visit number 4).

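### SAP 6.2 files early-withdrawal assessments under the next empty visit number whatever the study day, so vital signs and painful-area mapping are usually labelled with a later week or a week at which they are not planned

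*SAP*

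**What the plan says.** - **Reassignment rule (SAP 6.2).** The last assessment of an early withdrawal is stored as visit 90. Then: "By convention, for these subjects, the visit number will be reassigned to the next empty visit number". The worked example is "if a subject has Visit 1, 2, 3 and 90 entered in the database, the visit number 90 will be reassigned to visit number 4". Neither sentence mentions a date or study day.
- **What the tables show (SAP 6.2).** Listings include unscheduled visits and retests, but "for the description by visit in the tables, only the scheduled visits according to the protocol will be described".
- **What labels a visit (SAP 5.1.1.3).** By-visit summaries use the eCRF visit number. The visit list there includes Weeks 2, 4, 8, 10 and 14, which Protocol Attachment 1 (18.1) schedules as telephone contacts, as well as Weeks 6 and 12 and end of study.
- **Window (SAP 6.1).** "Visits can occur +/- three days around the scheduled date". This says when visits may take place. It is not applied to visit 90.
- **Closest-value rule (SAP 6.2).** "the closest non-missing reliable value to the scheduled visit will be used in the summary tables" covers retests of laboratory values, vital signs and ECG only.
- **When the withdrawal visit happens (Protocol 5.2.4).** At Week 16 within three days, or at any earlier time if the subject discontinues.
- **Planned post-dose timepoints.** Vital signs: Day 1 post-dose, Week 6 and end of study (SAP 5.8.5). Painful-area mapping: Week 6, Week 12 and end of study (SAP 5.7.4.1).

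**The concern.** A withdrawal assessment can fall on any day, but the rule gives it the label of the next slot in the sequence. Painful-area change is summarised by treatment group and measurement time (SAP 5.7.4.2) and vital signs by treatment group and timepoint (SAP 5.8.5). A value measured soon after dosing can therefore be tabulated as if it belonged to a later week, or be attached to a week at which nobody else has that measurement. In effect an early value is shifted forward without being declared as such.

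Early withdrawal is foreseen in this trial: Protocol 4.4 has a replacement rule for the first six weeks. About six subjects per arm are planned, so a single misplaced value can be visible in a summary. The rule is also incomplete for a subject who missed an earlier visit, because the example covers consecutive visits only and does not settle which empty number is next.

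**Working it through.** The plan gives no figure to reproduce. The check applies the rule to every possible withdrawal day.

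**Inputs and assumptions**
- Dosing is Day 1 (SAP 5.1.4). Week w is taken as Day 1 + 7w, so Week 6 = Day 43, Week 12 = Day 85 and Week 16 = Day 113.
- Withdrawal days run from Day 2 to Day 110: 110 − 2 + 1 = 109 days. Day 110 is three days before Day 113.
- All earlier visits were attended on their nominal day. Reassigned visit = first numbered visit with nominal day on or after the withdrawal day d. Error = nominal day − d.
- A value is correctly placed if the reassigned visit is planned for that parameter and the error is at most 3 days. The 3 days are borrowed from SAP 6.1 as a yardstick.
- The documents do not say whether telephone weeks have their own eCRF visit numbers, so both cases are counted.

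**Case 1: telephone weeks numbered (Weeks 2, 4, 6, … 16)**
- Vital signs: correct on Days 40–43 and 110, 4 + 1 = 5. At a planned week but more than 3 days early: Days 30–39 (Week 6) and 100–109 (end of study), 10 + 10 = 20. At a week with no planned vital signs: Days 2–29 and 44–99, 28 + 56 = 84.
- Mapping: correct on Days 40–43, 82–85 and 110, 4 + 4 + 1 = 9. More than 3 days early: Days 30–39, 72–81 and 100–109, 30 in all. Not planned: Days 2–29, 44–71 and 86–99, 28 + 28 + 14 = 70.
- Largest error: Day 30 filed at Day 43, 43 − 30 = 13 days.

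**Case 2: only clinic visits numbered (Weeks 6, 12, 16)**
- Vital signs: correct 5. More than 3 days early: Days 2–39 and 86–109, 38 + 24 = 62. Filed at Week 12, where vital signs are not planned: Days 44–85, 42.
- Mapping: correct 9. More than 3 days early: Days 2–39, 44–81 and 86–109, 38 + 38 + 24 = 100.
- Largest error: Day 2 filed at Day 43, 43 − 2 = 41 days.

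| Numbering | Parameter | Correct | Planned week, >3 days early | Week not planned |
|---|---|---|---|---|
| Telephone weeks numbered | Vital signs | 5 (4.6%) | 20 (18.3%) | 84 (77.1%) |
| Telephone weeks numbered | Mapping | 9 (8.3%) | 30 (27.5%) | 70 (64.2%) |
| Clinic visits only | Vital signs | 5 (4.6%) | 62 (56.9%) | 42 (38.5%) |
| Clinic visits only | Mapping | 9 (8.3%) | 100 (91.7%) | 0 |

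Giving the Day 2–7 contacts a single visit number of their own leaves the Case 1 counts unchanged. The percentages count days equally. They are not probabilities of withdrawal.

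**Weight of one subject.** Where the value lands in a populated row, it is 1/6 = 17% of a six-subject mean, or 1/7 = 14% if a replacement brings the arm to seven.

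**The case against.** The strongest reply is that little depends on this, and several parts of it stand.

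- **Size.** SAP 5.1.1.3 and Protocol Attachment 1 both give the telephone weeks their own place, which suggests that they are numbered. A Day 8 withdrawal would then be filed at Week 2 (Day 15), 15 − 8 = 7 days out, and not at Week 6, 43 − 8 = 35 days out. A reader might infer errors of four to six weeks as a matter of course. Those need clinic-only numbering, which the SAP list supports less well.
- **Loss from tables.** A reader might infer that values filed at a telephone week are dropped. The text does not say so. The scheduled-visits-only sentence is set against unscheduled visits and retests, and a renumbered visit 90 carries a scheduled number. A stray, sparse row is just as consistent with it.
- **Window.** The three days in SAP 6.1 are a conduct window, so the rule does not contradict an analysis window. The SAP states none.
- **Reach.** Spontaneous pain is recorded twice daily on the device (Protocol 9.1.3), so the primary endpoints need not depend on visit 90. QST and SF-36 are not scheduled at early discontinuation (Attachment 1), and physical examination and pregnancy tests are only listed. Tolerability has its own adverse-event tables and a listing of events leading to discontinuation. Mapping is not a protocol endpoint.
- **Transparency.** Listings carry dates and study days (SAP 5.1.4 and Appendix A5), visit dates and withdrawn subjects are listed (SAP 5.2), and no tests are planned.

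None of this supplies a rule that places visit 90 by day. Followed as written, the plan still puts most such values under the wrong label.

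**Conclusion.** The point holds as a minor one. The SAP 6.2 rule ignores study day, and no other section corrects it. Vital signs and painful-area mapping from early withdrawals are correctly placed only when the subject leaves on, or within three days before, a visit planned for that parameter: 5 of 109 possible days for vital signs and 9 of 109 for mapping, under either numbering.

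The size of the error depends on eCRF numbering that the documents do not give. With telephone weeks numbered, the more likely reading, a value shown at a planned week is up to 13 days early. Many values fall on weeks with no planned assessment, where they may appear as a stray row or be left out. With clinic visits only, the error reaches 41 days and one subject is about one-sixth of an arm's visit mean. That fraction does not apply to a value sitting alone in a stray row.

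A reader might go further and infer bias in the primary analgesic profile. The documents do not support that, for the reasons of reach given above. SAP 5.7.4.1 does not say whether the end time for SPID and AUE is taken from a relabelled visit, so no claim is made about those. The counts assume attendance on nominal days and a 3-day yardstick.

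**What to change.** Replace the renumbering sentence in SAP 6.2 with a date-based rule:

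- Assign visit 90 by actual study day to a visit planned for that parameter only if it lies within a stated analysis window. The three days already used for visit conduct would serve, but the SAP should state them as an analysis window.
- Otherwise show the value in a separate early-discontinuation row of the vital-signs and painful-area tables, by treatment group.
- State that sequence plays no part, which also settles the case of a missed earlier visit.

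The cost is SAP wording, a date-based mapping in the programming and one sparse row in each affected table. No data collection, visit or sample size changes.

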7 DERIVED DATA

QST data – Tactile detection thresholds

During the tactile detection test, the force (in g) recorded is in a logarithmic scale. To analyse the data, the values will be converted on a linear scale following the table below.

Filament	A	B	C	D	E	F	G	H	I	J	K	L	M	N	O	P	Q	R	S	T
Force (g)	0.008	0.02	0.04	0.07	0.16	0.4	0.6	1	1.4	2	4	6	8	10	15	26	60	100	180	300
Conversion	1	2	3	4	5	6	7	8	9	10	11	12	13	14	15	16	17	18	19	20

SF-36 Questionnaire – Score derivation

The SF-36 consists of 36 questions divided in 8 dimensions: General health, Physical functioning, Role physical, Role emotional, Social functioning, Bodily pain, Vitality, Mental health and one additional question on Reported health transition.

In each dimension, each question will be coded from 0 to 100, using the table below.

Question number	Original response	Analysis Value
1, 2, 6, 8, 11b, 11d	First modality: Excellent / Much better now than one year ago / Not at All / Definitely true	100
	Second modality: Very good / Somewhat better now than one year ago / Slightly / A little bit / Mostly true	75
	Third modality: Good / About the same / Moderately / Don't know	50
	Fourth modality: Fair / Somewhat worse than one year ago / Quite a bit / Mostly false	25
	Fifth modality: Poor / Much worse now than one year ago / Extremely / Definitely false	0
3a, 3b, 3c, 3d, 3e, 3f, 3g, 3h, 3i, 3j	First modality: Yes, Limited a Lot	0
	Second Modality: Yes, Limited a little	50
	Third modality: No, Not Limited at All	100
4a, 4b, 4c, 4d, 5a, 5b, 5c	First modality: Yes	0
	Second modality: No	100
7, 9a, 9d, 9e, 9h	First modality: None / All of the time	100
	Second modality: Very mild / Most of the time	80
	Third modality: Mild / A good bit of the time	60
	Fourth modality: Moderate / Some of the time	40
	Fifth modality: Severe / A little of the time	20
	Sixth modality: Very severe / None of the time	0
9b, 9c, 9f, 9g, 9i	First modality: All of the time	0
	Second modality: Most of the time	20
	Third modality: A good bit of the time	40
	Fourth modality: Some of the time	60
	Fifth modality: A little of the time	80
	Sixth modality: None of the time	100
10, 11a, 11c	First modality: All of the time / Definitely true	0
	Second modality: Most of the time / Mostly true	25
	Third modality: Some of the time / Don't know	50
	Fourth modality: A little of the time / Mostly false	75
	Fifth modality: None of the time / Definitely false	100

Within each dimension, scores will be derived as the mean of the responses, thus scores will range from 0 to 100, with higher score defining a more favourable health. Missing data will not be taken into account and will not be replaced. Table below presents the number of questions by dimension.

Area	Dimension	Numbers of questions
Functional status	Physical functioning	10
	Social functioning	2
	Role physical	4
	Role Emotional	3
Wellbeing	Mental health	5
	Vitality	4
	Bodily pain	2
Overall evaluation of health	General Health	5
	Reported health transition	1
TOTAL		36

SF-36 Questionnaire – Mapping rules between Version 2.0 and 1.0

Question	Version 2	Version 1	Mapping rules
During the past 4 weeks, have you had any of the following problems with your work or other regular daily activities as a result of your physical health?	Modalities used are the following: - All of the time - Most of the time - Some of the time - A little of the time - None of the time	Modalities used are the following: - Yes - No	Modalities from version 1 will be mapped as follow: - All of the time => Yes - Most of the time => Yes - Some of the time => Yes - A little of the time => Yes - None of the time => No
During the past 4 weeks, have you had any of the following problems with your work or other regular daily activities as a result of any emotional problems (such as feeling depressed or anxious)?	Modalities used are the following: - All of the time - Most of the time - Some of the time - A little of the time - None of the time	Modalities used are the following: - Yes - No	Modalities from version 1 will be mapped as follow: - All of the time => Yes - Most of the time => Yes - Some of the time => Yes - A little of the time => Yes - None of the time => No
These questions are about how you feel and how things have been with you during the past 4 weeks. For each question, please give the one answer that comes closest to the way you have been feeling.	Modalities used are the following: - All of the time - Most of the time - Some of the time - A little of the time - None of the time	Modalities used are the following: - All of the time - Most of the time - A good bit of the time - Some of the time - A little of the time - None of the Time	No change will be done

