6.3. Operator and training

The tests should be performed by a single trained operator for each patient.

7. Performing the tests:

Always perform the test in the same order below. Mark/ map the area of painful site for testing and identify the suitable non-painful/ contralateral site for testing. Always do test over the non-painful site and then do the painful site for comparison (unless mentioned otherwise below). Do all tests with the patients eyes closed. Explain to the patient before each test to ensure a consistent response and if required demonstrate the procedure on the patient.

Sensory Threshold (ST): Seventeen, progressively rigid, monofilament, von Frey fibers (filaments represent stimuli from 0.039 – 4386mN) will be used for this test. Test the area with von Frey’s filament, starting from the lowest/ thinnest monofilament. Each filament should be applied to the skin at a 90° angle with sufficient force to bend or bow the filament. The filament is held in place for 1.5 seconds and then removed. The exact threshold is found by repetitive testing ascending fibre sizes. The patient is instructed to respond “Yes” when a stimulus was felt. Each filament is applied up to 3 times in increasing filament thickness and the patient should say ‘Yes’ at least twice for the threshold filament.

Pain Perception Threshold (PPrT): This test is performed similar to ST but the response is the monofilament producing discomfort/ pain.

Static Mechanical Allodynia (SMA): This test is performed by applying the plastic base of a von Frey filament for 10 seconds with sufficient pressure, indenting the skin-testing area. This is recorded in a 11-point Numerical Rating Scale (NRS).

Dynamic (Brush evoked) Mechanical Allodynia (DMA): DMA is evoked by gently stroking the test area with a foam brush. This is recorded in a 11-point Numerical Rating Scale (NRS).

Temporal summation: This test is done only on the painful site. A baseline NRS score will be obtained from the patient with the vFF as part of the PPrT measurement. This fibre will be used for the test. The patient is given a repetitive stimulation consisting of 30 repetitions of a pressure stimulus applied for 1 second duration for 30 seconds. The magnitude of the stimulus is set at the level of the subjects' pressure pain threshold. Patients rate the pain intensity on a NRS at the end of the 30 seconds and this is repeated for up to 10 sets or until you or the patient decide to stop due to the level of discomfort.

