Change from baseline will also be derived at each timepoint for baseline assessment, for the painful area only.

- **Temporal summation** on painful area only: NRS score is recorded pre-stimulus and 10 attempts are performed after stimulus.
Change from baseline will also be derived at each time point as follows: NRS score from the last set of attempts – NRS pre-stimulation.
- **Tactile detection thresholds** on contralateral/non-painful area and on painful area: results (in g) will be assessed to determine sensory and pain perception threshold on each area.
Thresholds are assessed on a logarithmic scale. It will be converted to a linear scale for the analysis (see section 7).
Change from baseline will also be derived at each time point, for the painful area only.
- **Mechanical pain sensitivity and dynamic mechanical allodynia** on contralateral/non-painful area and on painful area: on each area, NRS-score will be assessed during static mechanical allodynia and dynamic mechanical allodynia.
Change from baseline will be derived at each time point, for the painful area only.
- **Pressure pain thresholds (PPT) (in kg/cm²)** on contralateral/non-painful area and on painful site: 3 readings of PPT, as well as their average, will be assessed in 4 positions, on each area. The global average of all the PPT values from all the positions will be derived for the painful and non-painful area.
Change from baseline on the global average PPT will also be derived for the painful area only.
- **Conditioned pain modulation (CPM)** on painful area will be performed and the following parameters will be determined:
 - a. 2 NRS scores: baseline and resulting NRS (cuff in situ).
 - b. Duration of cuff occlusion (in min:sec)
 - c. Clenching (Yes/No)
 - d. Pressure applied (in mmHg)
 - e. 3 PPT readings (in kg/cm²) and their average.CPM is assessed at the point on the painful area with the lowest PPT value from the previous test. A flag should be added if CPM is not evaluated at the lowest PPT position. Change from baseline on the average PPT for the painful area will also be derived.
- **Thermal detection and pain thresholds** on contralateral/non-painful area and on painful area including cold sensation (in °C; 4 replicates and the average), warm sensation (in °C; 4 replicates and the average), cold pain (in °C; 3 replicates and the average) and heat pain (in °C; 3 replicates and the average).

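### The 1–20 code for von Frey thresholds is a filament rank, not a linear scale: the same 2.5-fold change scores +1, +2 or +3, and the filament table differs from the protocol's

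*SAP*

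**What the plan says.** SAP 5.7.4.1 (QST, tactile detection thresholds) has sensory and pain perception thresholds recorded in grams on the painful and the non-painful area. It then says: "Thresholds are assessed on a logarithmic scale. It will be converted to a linear scale for the analysis". It adds: "Change from baseline will also be derived at each time point, for the painful area only".

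SAP 7 repeats the premise, stating that "the force (in g) recorded is in a logarithmic scale. To analyse the data, the values will be converted on a linear scale". Its table covers 20 lettered filaments, with these forces: "Force (g) 0.008 0.02 0.04 0.07 0.16 0.4 0.6 1 1.4 2 4 6 8 10 15 26 60 100 180 300". Below them, a second row codes the filaments by the whole numbers from 1 (lightest) up to 20 (heaviest).

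SAP 5.7.4.2 plans summary tables of values and changes from baseline by treatment group and visit, and plots in which arithmetic means are joined across visits for each group. SAP 5.1.2 makes mean, SD, median, quartiles and range the standard statistics. Force appears beside the filament reference on individual histograms, and individual QST assessments are listed.

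Protocol Attachment 4 (Sensory Threshold) describes the kit as "Seventeen, progressively rigid, monofilament, von Frey fibers", with stimuli from 0.039 to 4386 mN.

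**The concern.** A gram is already a linear unit. It is the spacing of the filament series that is roughly logarithmic. Replacing force by filament order would give an even log scale only if every filament were the same multiple of the one before. If the multiples differ, one step of the code stands for a different proportional change at different points of the series. A mean change from baseline then depends partly on where subjects start. Subjects in this trial may start at quite different thresholds, there are about six per arm, and SAP 5.7.1.2 plans no covariate adjustment.

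The second matter is practical. A conversion table works only if it lists the filaments that were applied, and the SAP's list differs from the protocol's in number and in range.

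**Working it through.** **Inputs.** Forces and codes: SAP 7. Filament count and range: protocol Attachment 4. Arm size of six: protocol 11.2 and SAP 2.3. One assumption is not in the documents: g means gram-force, so 1 g = 9.80665 mN.

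**1. Reproduce the code.** Sorting the 20 forces in ascending order and numbering them gives A = 1 to T = 20, exactly the SAP's conversion row. The code is the rank of the filament.

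**2. Is it linear in force?** One rank is worth 0.02 − 0.008 = 0.012 g at the bottom and 300 − 180 = 120 g at the top. R-squared of rank on force is 0.451. It is not.

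**3. Is it linear in log force?** The step is log10(F[k+1]/F[k]).

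- Smallest: 8 to 10 g, log10(1.25) = 0.097.
- Largest: 0.008 to 0.02 g and 0.16 to 0.4 g, log10(2.5) = 0.398.
- Spread: 0.398/0.097 = 4.1-fold.
- An even log scale over this range would have a constant ratio of (300/0.008)^(1/19) = 1.74.
- R-squared of rank on log10 force is 0.987.

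So the rank is close to log-linear over the whole range but uneven from step to step.

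**4. Same change, different score.**

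| From → to (g) | Fold change | Rank change | log10 change |
|---|---|---|---|
| 0.008 → 0.02 | 2.5 | +1 | 0.398 |
| 0.16 → 0.4 | 2.5 | +1 | 0.398 |
| 0.4 → 1 | 2.5 | +2 | 0.398 |
| 4 → 10 | 2.5 | +3 | 0.398 |
| 6 → 15 | 2.5 | +3 | 0.398 |
| 0.07 → 0.4 | 5.7 | +2 | 0.757 |

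The last two rows show that, for individual subjects, a smaller proportional change can receive the larger score.

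**5. Effect on an arm mean.** If one of six subjects scores +3 rather than +1 for the same 2.5-fold change, the mean moves by (3 − 1)/6 = 0.33 rank.

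**6. How often would arms change order?** As an illustration, two arms of six were simulated with baselines spread evenly over filaments 4–15, an SD of change of 2 ranks and a true difference of 1 rank, all assumed. The arm difference in mean rank and in mean log10 force correlated at 0.96 and had opposite signs in 4–5% of runs. Spreading baselines over filaments 2–17, or using an SD of 3 ranks, also gave 4–5%.

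**7. The two filament sets.**

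| | Count | In mN | In g |
|---|---|---|---|
| Protocol Attachment 4 | 17 | 0.039–4386 | 0.039/9.80665 = 0.0040 to 4386/9.80665 = 447 |
| SAP 7 | 20 | 0.008 × 9.80665 = 0.078 to 300 × 9.80665 = 2942 | 0.008–300 |

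The counts differ without any assumption. With g as gram-force, the protocol range extends beyond the SAP table at both ends.

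**The case against.** Several points on the other side have force.

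- **Weight.** The protocol's secondary QST endpoint is the stimulus-evoked NRS score. Tactile thresholds are an additional QST parameter in the SAP, and they feed no primary endpoint, test or decision rule. This stands and limits the importance of the point.
- **Closeness to log force.** The SAP recognises the logarithmic spacing, and the rank is a fair overall approximation. This stands too. Change from baseline, however, is a local comparison, and the unevenness is local.
- **Resolution.** The test steps up filament by filament, so a threshold is known only to lie between neighbours. A one-step move is not a measured 25% or 131% change, and log10 of the filament force has the same limit. That is fair for single steps, but it does not explain why one 2.5-fold change spans one step and another three.
- **Other displays.** Medians and quartiles are also planned, and force is visible for each subject. A reader could rebuild fold changes, but no planned group summary does so, and medians of rank changes have the same uneven steps.

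Two stronger readings are tempting. A reader might infer that the coding is likely to reverse the order of the arms. Reversal is possible, but nothing in the documents makes it likely, and under the assumptions above it was uncommon. A reader might also infer that extreme thresholds will become missing. Neither document says so. It would follow only if the protocol kit were used with the SAP table. The SAP records grams and names filaments A to T, so its table may well describe the kit actually used, and then no reading lacks a code.

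**Conclusion.** The code in SAP 7 is ordinal and is mislabelled as linear. Steps differ 4.1-fold on the log scale, so equal proportional changes score +1 to +3. The consequence is modest: a local distortion of arm means and changes from baseline for one descriptive secondary QST parameter, of the order of 0.33 rank in an arm of six for one affected subject. This takes the converted values to be what the group summaries use, as SAP 5.7.4.1 indicates.

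The filament sets are unreconciled: 20 against 17, with different ranges if g means gram-force. The documents do not settle which kit was used, so a loss of readings at the extremes is conditional on that.

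**What to change.** 1. In SAP 5.7.4.1, 5.7.4.2 and 7, take log10 of the force of the recorded filament as the analysis value. Report the geometric mean force by arm and visit, and change from baseline as the difference in log10 force, back-transformed to a fold change. Every 2.5-fold change then scores 0.398 wherever it starts.
2. Keep the 1–20 code for listings only. If it stays in the tables, describe it as ordinal, lead with median and quartiles, and remove the statement that it is linear.
3. State in SAP 7 which kit was used, and reconcile the table with protocol Attachment 4. If the protocol kit was used, give all seventeen filaments a force in the table. If the SAP's kit was used, record that it differs from Attachment 4. Filament identity also matters for temporal summation, where the pain-threshold filament is reused and shown on the individual graphs.

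Cost: one derivation line, new table labels and a sentence on the kit. Force is already recorded, so no new data are needed. Readers will need a short note on interpreting fold changes.
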